- Patient gender
- Patient race/ethnicity
- Patient primary insurance
- Nursing staff who roomed the patient (designated by a unique study identifier)
- Whether patient used mPATH-CheckIn program (Y/N)
- Whether nursing staff used mPATH Nursing Module to transmit mPATH data to WakeOne (Y/N)
- Whether patient has a diagnosis of depression in the problem list in the EHR (Y/N)
- Whether patient has an antidepressant medication listed in the active medication list (Y/N)
- Results of depression screening items
- Results of fall risk screening items
- Results of safety at home screening items

The study dataset will be maintained using the procedures outlined in **Section 8.0 (Confidentiality and Privacy)**. Of note, we are taking the following additional safeguards to further protect patient confidentiality:

1. Dates of clinic visits will be designated using numbers relative to each clinic's launch date, rather than using the actual date
2. Clinics will be designated with a unique study clinic identifier instead of clinic name
3. Nursing staff will be designated with a unique study identifier instead of actual name

Definition of Time Periods

- The day a clinic launches mPATH will be designated as that clinic's Day 0
- The "pre" time period will be Days -60 to -1 (the 60 day period before mPATH Launch)
- The "post" time period will be days 14 to 73 (the 60 day period commencing 2 weeks after mPATH Launch)

Outcome Measures

Protocol version date
7/29/2021

EFFECTIVENESS AND IMPLEMENTATION OF MPATH-CRC: A MOBILE HEALTH SYSTEM
FOR COLORECTAL CANCER SCREENING
Wake Forest Baptist Comprehensive Cancer Center (WFBCCC)
WFBCCC # TBD

Primary outcome: The primary outcome will be the proportion of patients seen in each time period (“pre” vs. “post”) who screen positive for depression, fall risk, or safety concerns at home.

Secondary outcomes: Secondary outcomes will include the proportion of patients in each time period who:

- Screen positive for depression using the PHQ-2 items. In addition, the outcomes below will be assessed:
 - Have a PHQ9 score >14 (indicating moderately severe depression or severe depression)
 - Have a PHQ9 score >19 (indicating severe depression)
 - Have a PHQ9 score >14 and are not currently taking a medication for depression
 - Have thoughts of self-harm
- Screen positive for fall risk at home. In addition, the outcomes below will be assessed:
 - Have fallen in last 6 months
 - Have had a fall with injury

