- Screen positive for safety concerns at home. In addition, the outcome below will be assessed:
 - Report that conflicts turn into fights

Analytic plan

Our primary analysis will compare the proportion of patients seen in the “pre” time period to the “post” time period who screen positive for either depression, fall risk, or safety at home. If a patient is seen more than once in a given time period, only the patient’s first visit in that time period will be included in the analyses. We will estimate the proportion who screen positive for each time period and report along with 95% confidence intervals. A chi-square test will be used to provide an unadjusted comparison between the “pre” and “post” proportions. Logistic regression models will then be used to compare the “pre” and “post” proportions while controlling for clinic and patient demographic variables. We will use the same analytic methods for our secondary outcomes. We will also conduct a sensitivity analysis for our primary outcome where we consider all patients’ visits during a given time period (and not limit analyses to a patient’s first visit in the time period only). For this sensitivity analysis, we will compare the proportion of patients who meet our primary outcome definition at any visit during the “pre” and “post” time periods.

Analytic adjustments due to COVID19 pandemic: Due to the COVID19 pandemic, all practices stopped using mPATH in March 2020, which is prior to the closure of the 60-day “post” time period for clinics #5 and #6 in our sample. Therefore, we will truncate Protocol version date

7/29/2021

EFFECTIVENESS AND IMPLEMENTATION OF MPATH-CRC: A MOBILE HEALTH SYSTEM
FOR COLORECTAL CANCER SCREENING
Wake Forest Baptist Comprehensive Cancer Center (WFBCCC)
WFBCCC # TBD

the “post” time period for these two clinics to 30 days. To determine if this truncated time period affected our overall results, we will conduct the following sensitivity analyses: (1) limiting the analyses to only the first 4 clinics to enroll, and (2) limiting data collection to 30-days post- for all 6 clinics.

Protocol version date
7/29/2021

EFFECTIVENESS AND IMPLEMENTATION OF MPATH-CRC: A MOBILE HEALTH SYSTEM
FOR COLORECTAL CANCER SCREENING
Wake Forest Baptist Comprehensive Cancer Center (WFBCCC)
WFBCCC # TBD

Protocol version date
7/29/2021

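### The COVID adjustment shortens only the post window, so the any-visit sensitivity analysis (clinics 5 and 6) and COVID sensitivity analysis 2 (all six clinics) compare 60 pre days with 30 post days

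*Combined protocol and SAP*

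**What the plan says.** All references are to Appendix D of the combined protocol and SAP.

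- **Windows (Definition of Time Periods).** The pre "time period will be Days -60 to -1 (the 60 day period before mPATH Launch"; the post window is Days 14 to 73. Both apply to every clinic.
- **Primary analysis (Analytic plan).** For a patient with several visits in a period, only the "first visit in that time period will be included in the analyses". Pre and post are compared by an unadjusted chi-square test and then by logistic regression "while controlling for clinic and patient demographic variables".
- **Any-visit sensitivity analysis (Analytic plan).** All visits count: "we will compare the proportion of patients who meet our primary outcome definition at any visit during" each period.
- **COVID adjustment (Analytic plan, last paragraph).** The plan truncates the post "time period for these two clinics to 30 days", meaning clinics 5 and 6. "To determine if this truncated time period affected our overall results", it adds two analyses: (1) "limiting the analyses to only the first 4 clinics to enroll", and (2) "limiting data collection to 30-days post- for all 6 clinics".

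No sentence shortens the pre window in any of these analyses.

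**The concern.** Screening is repeated at each provider visit, so the chance of at least one positive result depends on how long a patient is observed. In clinics 5 and 6 the any-visit analysis sets 60 days of opportunities before launch against 30 after. The mismatch lies within clinic, so a clinic term does not absorb it.

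The any-visit analysis is the plan's check on the first-visit rule. If it disagreed with the primary result because of window length alone, readers could take that for a real difference between the two outcome definitions.

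Sensitivity analysis 2 is meant to show whether truncation mattered, yet it extends the 60-against-30 mismatch to every clinic. A shorter window picks up relatively more frequent attenders. If the result moved, one could not tell truncation from unequal windows. Sensitivity analysis 1 is matched at 60/60 but covers four clinics, so no planned analysis has equal windows in all six.

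**Working it through.** **Window lengths.** Pre: -1 - (-60) + 1 = 60 days. Post: 73 - 14 + 1 = 60 days. Both agree with the plan. Truncated post, counted from Day 14: Days 14 to 43, 43 - 14 + 1 = 30 days.

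**Assumed inputs.** Appendix D gives no visit rate, positivity or clinic size. I assume six equal clinics, Poisson visits at 3 or 6 a year, positivity p = 0.20 per visit and no true effect. A share c of patients give the same result at every visit; the others' results are independent between visits.

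**Any-visit proportion.** With m = annual rate × T/365, P(seen) = 1 - exp(-m), and

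a(T) = c·p + (1 - c)·[1 - exp(-p·m)]/[1 - exp(-m)].

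Example, 3 visits a year, c = 0:
- T = 60: m = 0.4932, a = [1 - exp(-0.0986)]/0.3893 = 24.13%.
- T = 30: m = 0.2466, a = [1 - exp(-0.0493)]/0.2185 = 22.02%.
- Difference within clinics 5 and 6: -2.11 points.

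**Clinic-adjusted difference.** Let r be patients seen in 30 days divided by patients seen in 60: 0.561 at 3 visits a year, 0.621 at 6. The weights n1·n0/(n1 + n0) are 0.5 for a full clinic and r/(1 + r) for a truncated one. At 3 a year: 2 × 0.3595 × (-2.11)/(4 × 0.5 + 2 × 0.3595) = -0.56. The ORs come from a binomial logistic model with clinic terms and a post term, fitted to expected counts.

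| Visits/year | c | Clinics 5 and 6 (points) | Clinic-adjusted (points) | OR |
|---|---|---|---|---|
| 3 | 0 | -2.11 | -0.56 | 0.970 |
| 3 | 0.5 | -1.05 | -0.28 | 0.984 |
| 3 | 0.8 | -0.42 | -0.11 | 0.993 |
| 6 | 0 | -4.42 | -1.23 | 0.941 |
| 6 | 0.5 | -2.21 | -0.61 | 0.967 |
| 6 | 0.8 | -0.88 | -0.25 | 0.986 |

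Within this model c = 0 gives the largest shift. Some persistence is likely, since one fall item looks back 6 months, longer than either window.

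**Sensitivity analysis 2, first visit.** If positivity is unrelated to visit frequency, the artefact is exactly zero. Otherwise suppose 20% of patients attend often and 80% attend twice a year.
- *Mild* (6 a year; positivity 25% against 20%): frequent attenders are 35.9% of those seen in 60 days and 39.1% in 30. First-visit positivity goes from 21.79% to 21.96%, +0.16 points.
- *Strong* (12 a year; 35% against 15%): the share goes from 43.4% to 50.8%. Positivity is 15 + 20 × 0.4344 = 23.69% against 15 + 20 × 0.5084 = 25.17%, +1.48 points.

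**Main first-visit analysis, clinic-adjusted, same mixtures.** Only clinics 5 and 6 are mismatched. With r = 0.570 (mild) and 0.622 (strong), their combined weight is about 0.27 and 0.28, giving +0.04 and +0.41 points.

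**Sign of the any-visit shift.** With 35% against 15% positivity, frequent attenders at 6 or 12 visits a year and c = 0.8, the shift in clinics 5 and 6 is +0.11 or +0.52 points. Under independence the 12-a-year case gives -3.31.

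**Pooled chi-square, first visit.** Suppose 15% positivity in clinics 1 to 4 and 20% in clinics 5 and 6. Pre: (4 × 15 + 2 × 20)/6 = 16.67%. Post at r = 0.561: (4 × 15 + 2 × 0.561 × 20)/(4 + 2 × 0.561) = 16.10%, a shift of -0.57 points (-0.48 at r = 0.621). With 25% in clinics 5 and 6 it is -1.14 (-0.96).

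**The case against.** The strongest objections are these.

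- **The any-visit sign is not fixed.** This stands. A reader might infer that the artefact always lowers post and so can only hide a gain in detection. The documents give no visit rates or persistence to support that, and the strong mixture with 80% persistence reverses it.
- **The first-visit primary analysis is not untouched.** This stands in part. Under the strong mixture at c = 0.5 the adjusted first-visit shift (+0.41) exceeds the adjusted any-visit shift (-0.25) in size. The pooled chi-square also changes clinic mix: at an assumed 1,000 patients per clinic, the 15% against 20% and 15% against 25% cases give false-positive rates of about 13% and 35%. The planned clinic-adjusted model removes the clinic-mix effect, though not selection by visit frequency. Conversely, a reader might infer that the primary result is invalid. The documents do not support that either: one visit per patient removes the repeat-opportunity problem, and what remains is zero unless visit frequency is related to positivity.
- **Sensitivity analysis 1 may already cover the any-visit measure.** It limits the analyses, in the plural, so this reading is possible. It would give a matched 60/60 check, but for four clinics only. Equally, one should not infer that sensitivity analysis 2 is repeated under the any-visit definition; the plan does not say so.
- **Sensitivity analysis 2 is sound when visit frequency and positivity are unrelated.** True, and a stable result would be reassuring. The weakness appears only if the result moves, which is what the analysis exists to interpret.
- **The effect is small and confined to sensitivity analyses.** True, and the severity reflects it.

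**Conclusion.** The point holds as a minor flaw. As written, the any-visit analysis compares unequal windows within clinics 5 and 6, and sensitivity analysis 2 does so in all six clinics.

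- **Any-visit analysis:** about -0.1 to -1.2 points clinic-adjusted (OR 0.99 to 0.94) with no true effect. Post is usually lowered, but the sign can reverse.
- **Sensitivity analysis 2:** zero if visit frequency is unrelated to positivity, and about +0.2 to +1.5 points under the mixtures shown.
- **Clinic-adjusted first-visit analysis:** little affected, 0 to about +0.4 points under the same mixtures.
- **Unadjusted chi-square:** shifts by about 0.5 to 1.1 points if clinics 5 and 6 differ in base rate by 5 to 10 points, downwards if their rate is the higher one.

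The asymmetry of the windows is certain from the text. Every magnitude rests on assumed rates.

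**What to change.** 1. In the any-visit analysis, use Days -30 to -1 against Days 14 to 43 for clinics 5 and 6, and keep 60/60 for clinics 1 to 4.
2. In sensitivity analysis 2, use the same matched 30-day windows in all six clinics and state the day numbers.
3. Base the conclusion on the clinic-adjusted model and report the pooled chi-square as descriptive.
4. Leave the windows of the main first-visit analysis and of sensitivity analysis 1 as planned.

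Equal windows remove the window-length artefact whatever its sign.

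**Cost.** A few sentences and no new data, since visits are already dated relative to launch. In the any-visit analysis, matching drops 1 - r = 38 to 44% of pre-period patients in clinics 5 and 6. The clinic-adjusted interval widens by √[(2 + 2r/(1 + r))/(2 + r)] = 1.030 (3 visits a year) or 1.027 (6), about 3%. Sensitivity analysis 2 widens by √[2/(1 + r)] = 1.132 or 1.111, and 1.139 at 2 visits a year (r = 0.541), so 11 to 14%. The main analysis loses no patients.
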